#### INFORMED CONSENT AND ASSENT PROCEDURES

Consent and assent is obtained at different levels. For community gatekeepers verbal and written informed consent will be obtained before participating in this study. All participants (community gatekeepers and caregivers) will be given the name and number of the study contact person in Uganda in case they have further questions, or wish to withdraw from the study. All participants will have the right to withdraw from the study and without obligation to provide a reason. Upon detection by a trained community gatekeeper – all caregivers, children and adolescents will first receive a verbal summation of the project and are asked for their verbal consent/assent to collect and release their information for study purposes. Information will only be documented if both the caregiver and child/adolescent's consent. For caregivers, children and adolescent that seek help after being detected the clinical team will hand out an information letter about the project ask them to sign a release of information form that permits TPO share de-identified data with the research team regarding how many children, adolescents and caregivers sought help as a result of the CCDT, and to share the routinely collected service utilization data. Caregivers, or children/adolescents that do not consent to the sharing of data will not be included in the study, but will continue to be involved in any service delivery at any time.

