# **Outcome measures**

#### Primary outcome measure

The primary outcome is utilization of TPO's mental healthcare services among children and adolescents detected by the CCDT. Utilization in this study will be defined as initial encounters with TPO's mental healthcare among children and adolescents 6-18 years old or their caregivers, or re-entry into services for children and adolescents that have not been using TPO's services for 6 months. This is measured in two ways:

(1) Service utilization data: the number of children and or adolescents aged 6-18 years old that seek mental healthcare services from TPO, compared to utilization rates of practice-as-usual (i.e., during the pre-CCDT period). TPO's routinely collected monthly mental health service utilization data will be used for this. Following routine practices, upon intake, TPO's clinical team completes a 'case registration form' (see Annex 4.1).

- (2) The proportion of children and adolescents detected by the CCDT as in need of mental healthcare that seeks help at TPO. Two data sources will be used and compared for this:
  - a. Detection data: number of detected cases per gatekeeper. Gatekeepers will be trained in keeping a log of the number of detected children while using the CCDT (see Annex 4.2). Gatekeeper logbooks will be collected bi-weekly by one of WCH's facilitators attached to the zone and handed over the project officers who will be trained in entering the data in a digital master sheet.
  - b. Service utilization data: Number of cases contacting TPO as a result of a community gatekeeper trained in the CCDT handing out a referral card. The same 'monthly mental health service utilization data' (see outcome 1 above) will be used for this. TPO's clinical team will be trained to ask all new clients (children, adolescents or caregivers) an intake question regarding the reason for seeking help (including the community gatekeeper handing out the referral card as one of the options). This data is entered by the clinical psychologist in the 'case registration form' used upon entry.

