## Randomization

Due to the community-based nature of the approach (i.e., implemented at the level of the zone) and integration of the CCDT into routine practice, randomization takes place at the zone level.

Data is therefore collected per zone, instead of on the individual child, adolescent or caregiver level. Each zone will be randomized to a sequence and start timing for when the CCDT will be introduced there using a random number generator in Stata, Version 17. Randomization will be done by the lead statistician based in the USA.

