## Caregivers, children and adolescents

Informed consent/assent will be obtained at two levels:

• By gatekeepers, at community level upon detection: This study will be integrated in routine practices and community gatekeepers will engage caregivers, children and adolescents as they would usually do in routine practice. They visit the family and provide information about TPO's services and encourage help-seeking. At this stage, there is no engagement in any study activity yet, however some information will be collected for study purposes. Gatekeepers will therefore provide a verbal summary of the project to caregivers, adolescents and children upon detection and help-seeking encouragement (see Annex 3.2). After providing this information, gatekeepers will ask verbal consent/assent to document and release their

information to the study team for study purposes. Information will only be documented if both the caregiver and child/adolescent give their verbal consent. Caregivers, or children/adolescents that do not consent to the sharing of data will not be included in the study, but will continue to be involved in any service delivery they need—if they desire to make use of these services. If a child/adolescent is detected but there is no caregiver available, they will be provided similar information regarding help-seeking but their data will not be used. For caregivers, adolescents and children that consented, gatekeepers will record the date of verbal consent and document the child's and family name, contact details, age, version of the CCDT used and if it concerns a new or an old detection in their logbook.

• By clinical team, at service level, upon entry to care: consent will be sought from caregivers/parents of children below 17 years and adolescents, and assent form for children between 6 to 17 years, that seek help at TPO. The clinical team will provide information about the study and ask for consent to document and release their de-identified information with WCH for study purposes (see Annex 3.3 and 3.4). Caregivers, or children/adolescents that do not consent to the sharing of data will not be included in the study, but will continue to be involved in any service delivery at any time. Since it concerns routinely collected data, their family name, age and phone number is needed in order to delete their information and exclude it from analysis.

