#### DATA COLLECTION AND PROCESSING

#### Description of data collected

Both quantitative and qualitative data will be collected.

Quantitative data

Quantitative data will be collected at two levels:

- 1) Detection data Gatekeepers will be provided with a logbook in which they will record the information about the detection (see Annex 4.2). A unique study ID will be created for each new case, this code will be linked to the gatekeepers' initials and cannot be traced back to the individual. The following information will be collected by gatekeepers:
  - o Study ID
  - Child's demographic information: age, gender, status (refugee/host), village, zone and settlement of residence
  - Contact details family
- Version of the CCDT used (i.e., the CCDT vignette that matched their observations)
- o Date of detection and engagement
- Date of verbal consent/assent obtained

This data will be collected in the zones where the CCDT is introduced, from the moment that the gatekeepers start using the CCDT, until the end of the project duration (i.e., April, 2023).

- 2) Service utilization (TPO) routine data will be collected at TPO for all clients seeking care. An anonymized client code will be assigned and used as the only identifier. The following variables will be collected in the Case Registration Form (see Annex 4.1):
  - Client ID
  - Demographic information: age, gender, status (refugee/host), village, zone and settlement of residence
  - Referral type: through CCDT or routine
    - This will be obtained through the referral card handed out by the gatekeeper using the CCDT (i.e., 'someone in the community approached me, handed out a referral card and encouraged me to seek help here')
  - Date of intake
  - Type of visit: new, re-entry or recurring/maintenance visit.
  - Mental health diagnosis
  - Service or type of treatment provided by TPO, or referral made

If treatment was initiated and completed.

This data will be collected from the beginning of the study in all zones, until the end of the project duration (i.e., April, 2023). A study specific data extraction sheet will be developed which will be used to collect all the information according to the primary and secondary outcomes.

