# Monitoring (quality control of the study)

Monitoring of the trial implementation and research will be done at three levels:

- Settlement level: monitoring at service level will be done by clinical psychologists. They will ensure that all registers all well filled and completed, all children referred are captured. The right code is assigned.

- Coordination level: monitoring at the coordination level will be done by WCH's program manager and M&E managers. They will ensure that all master sheets are complete.
- Regulatory level: during routine review of patient registers by clinical psychologists, completed participants consents will also be reviewed to ensure completeness and to ensure that every child/adolescent has a consent or assent signed before any data collection procedure. During monthly visits to the field, the research coordinator will also review 10% of the completed participants consents and registers. Any regulatory monitoring by the ethics committee will be communicated and planned on time by the concerned parties.

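### Clients who refuse data sharing are deleted from the primary utilization count, so any change in consent that starts at CCDT introduction becomes part of the IRR

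*Protocol*

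**What the plan says.** **Source of the count.** Under Primary outcome measure, the count covers first encounters with TPO, or re-entry after six months away, at ages 6-18. The source is explicit: "TPO's routinely collected monthly mental health service utilization data will be used for this". The Statistical Analysis plan section models it by mixed-effects Poisson regression with the log of each zone's child population as offset. The fixed effects are CCDT, time, and CCDT by time since cross-over.

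**Deletion.** Under Informed Consent and Assent procedure (Caregivers, children and adolescents), those who do not agree to data sharing are left out of the study. Because the data are routine, "their family name, age and phone number is needed in order to delete their information and exclude it from analysis".

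**Who is asked at TPO.** The same section covers those who seek help at TPO: "consent will be sought from caregivers/parents of children below 17 years and adolescents, and assent form for children between 6 to 17 years". Monitoring (quality control of the study) wants assurance that "every child/adolescent has a consent or assent signed before any data collection procedure". The summary's consent section is narrower: "For caregivers, children and adolescent that seek help after being detected the clinical team will hand out an information letter about the project". Ethical considerations, in the main body, uses the same narrower description.

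**An extra step under CCDT only.** On detection, the gatekeeper summarises the project and asks for agreement: "Information will only be documented if both the caregiver and child/adolescent give their verbal consent". If no caregiver is available, the detected child still receives the help-seeking information, but the child's data are not used.

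**Statements pointing the other way.** Description of data collected says that "routine data will be collected at TPO for all clients seeking care". Randomization says: "Data is therefore collected per zone, instead of on the individual child, adolescent or caregiver level".

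**The concern.** The objective concerns use of services, but the deletion rule turns the outcome into use of services by people who also agree to release their data. If the agreeing share were the same with and without the CCDT, this would cost only some counts. The protocol gives reason to doubt that it is the same. After cross-over, some clients reach TPO having already heard about the project from a trusted gatekeeper and been asked for verbal agreement. Control-period clients have had neither. Depending on which consent section is followed, routine clients may not be asked at all.

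A shift of this kind begins in each zone when the CCDT begins, so it lies along the treatment indicator. Because the protocol describes no count of refusals, it could be neither bounded nor corrected after the records are deleted.

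**Working it through.** **Plan's own figures.** The protocol states no consent rate, so there is none to reproduce. The yardstick is the 20% difference in utilization that Sample Size is built to detect, i.e. an IRR of 1.20. That calculation reproduces with Poisson variance and two-sided alpha 0.05 (assumed). Per arm, (1.960 + 1.282)² × (17.1 + 20.52) / 3.42² = 33.8 zone-months. The stepped-wedge design effect for seven steps at ICC 0.115 is 0.249, and 33.8 × 2 × 0.249 = 16.8 zones. The planned 28 zones are therefore consistent with power above 90% for 1.20.

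**Where consent enters.** Let c0 and c1 be the shares of eligible clients whose records remain in the count in control and CCDT periods. The expected count is population × rate × c, and the offset removes only the population. Hence

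observed IRR = true IRR × c1/c0.

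On the log scale consent adds log c. A stable difference between zones goes into the zone intercept, and a drift common to all zones goes into the time term. A change that starts at cross-over coincides with the CCDT term and remains. A ratio c1/c0 of 1/1.20 = 0.833 (for example 0.90 falling to 0.75) would hide the whole planned effect.

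**By referral route.** Let s be the CCDT-referred share of post-CCDT clients, and c_r and c_d the consent shares of routine and CCDT-referred clients. With c0 = c_r,

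observed IRR = true IRR × [1 + s × (c_d/c_r − 1)].

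If only detected clients are asked, c_r = 1.

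**Range for s (assumed).** At a true IRR of 1.20 with CCDT clients purely additional, s = 0.20/1.20 = 1/6. At s = 1/2, routine attendance is 0.5 × 1.20 = 0.60 of baseline, i.e. substantial substitution of routine entry by CCDT referral.

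**Results at a true IRR of 1.20 (all consent rates assumed):**

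| Who is asked | c_r | c_d | s = 1/6 | s = 1/2 |
|---|---|---|---|---|
| All, equal consent | any | same | 1.20 | 1.20 |
| All | 0.80 | 0.95 | 1.24 | 1.31 |
| All | 0.95 | 0.98 | 1.21 | 1.22 |
| All | 0.90 | 0.70 | 1.16 | 1.07 |
| Only detected | 1.00 | 0.80 | 1.16 | 1.08 |

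Worked case, second row: 0.95/0.80 − 1 = 0.1875. Then 1.20 × (1 + 0.1875/6) = 1.24 and 1.20 × (1 + 0.1875/2) = 1.31. Last row: 1.20 × (1 − 0.20/6) = 1.16 and 1.20 × (1 − 0.20/2) = 1.08.

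**With all encounters counted,** c0 = c1 = 1 and the observed IRR equals the true IRR.

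**The case against.** The strongest reply is that no consent rate appears anywhere, so neither the size nor the direction of bias can be stated. This stands. High and similar consent leaves almost nothing, as the 95%/98% row shows.

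Four stronger readings are tempting, and the documents do not support them.

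- *The bias is as large as the target effect.* In the table the shift from 1.20 runs from about 0.01 to 0.13. Under the 80%/95% and detected-only assumptions it is about a fifth of the 0.20 target if CCDT clients are purely additional, and up to about 60% with half the clients CCDT-referred.
- *An ineffective CCDT would appear effective.* Through referral route alone, this needs CCDT-referred clients to replace routine ones while total attendance stays flat. Without replacement, no effect means s = 0 and the IRR stays at 1.00.
- *The direction is known.* Prior contact with a gatekeeper may raise consent. But the rule on detected children without a caregiver, if carried through to TPO records, removes CCDT clients only and pulls the other way.
- *Only CCDT clients can be deleted.* The fuller procedure, the monitoring section and the titles of Annexes 3.3 and 3.4 carry no such restriction. The narrower wording is an inconsistency to resolve, not an established rule.

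It may also be said that collection for all clients, and per zone, means refusers stay in the totals. The explicit deletion rule contradicts that. The release form is also described as what permits sharing of how many sought help because of the CCDT, and of the routine utilization data.

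Finally, a separate analysis plan might handle refusals. It could not recover deleted records of which no tally was kept.

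**Conclusion.** The point holds in a limited form. The protocol deletes refusers from the data that supply the primary count, keeps the full population as denominator, and makes the consent route differ between conditions. The IRR is therefore multiplied by the ratio of consent shares. The model absorbs stable zone differences and common trends in that ratio, but not a change tied to CCDT status.

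Size and direction are unknown, and the bias is nil if consent is equal. The illustrations, from 1.07 to 1.31 for a true 1.20, rest on assumed consent rates and an assumed CCDT share of 1/6 to 1/2. The case for change does not depend on any one of them. It rests on the asymmetry being written into the procedure, with no provision to measure it.

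**What to change.** 1. Define the primary count as the anonymous zone-month total of all new and re-entry clients aged 6-18 in TPO's records, regardless of study consent and subject to ethics committee agreement. Keep consent and assent for individual-level records such as diagnosis, treatment and linkage to detection.
2. If the committee does not agree, have TPO report the number of refusals by zone, month and referral route. Add them to the count, or at least use them in a sensitivity analysis of the IRR.
3. Reconcile the summary's consent section and Ethical considerations with the consent procedure and the monitoring section, so that the same clients are asked in both conditions. State whether the rule on detected children without a caregiver applies to the logbook only or also to TPO records.

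The cost is one ethics submission and minor changes to the consent wording and the extraction sheet. The case registration form already records zone, intake date, visit type and referral type for every client, so the total needs no new data collection.

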#### DATA COLLECTION AND PROCESSING

#### Description of data collected

Both quantitative and qualitative data will be collected.

Quantitative data

Quantitative data will be collected at two levels:

- 1) Detection data Gatekeepers will be provided with a logbook in which they will record the information about the detection (see Annex 4.2). A unique study ID will be created for each new case, this code will be linked to the gatekeepers' initials and cannot be traced back to the individual. The following information will be collected by gatekeepers:
  - o Study ID
  - Child's demographic information: age, gender, status (refugee/host), village, zone and settlement of residence
  - Contact details family
- Version of the CCDT used (i.e., the CCDT vignette that matched their observations)
- o Date of detection and engagement
- Date of verbal consent/assent obtained

This data will be collected in the zones where the CCDT is introduced, from the moment that the gatekeepers start using the CCDT, until the end of the project duration (i.e., April, 2023).

- 2) Service utilization (TPO) routine data will be collected at TPO for all clients seeking care. An anonymized client code will be assigned and used as the only identifier. The following variables will be collected in the Case Registration Form (see Annex 4.1):
  - Client ID
  - Demographic information: age, gender, status (refugee/host), village, zone and settlement of residence
  - Referral type: through CCDT or routine
    - This will be obtained through the referral card handed out by the gatekeeper using the CCDT (i.e., 'someone in the community approached me, handed out a referral card and encouraged me to seek help here')
  - Date of intake
  - Type of visit: new, re-entry or recurring/maintenance visit.
  - Mental health diagnosis
  - Service or type of treatment provided by TPO, or referral made

If treatment was initiated and completed.

This data will be collected from the beginning of the study in all zones, until the end of the project duration (i.e., April, 2023). A study specific data extraction sheet will be developed which will be used to collect all the information according to the primary and secondary outcomes.

#### Qualitative data

Qualitative feedback from community gatekeepers who will be using the using the tool to understand the acceptability, appropriateness and feasibility of using the CCDT will be collected during the pre-implementation FGD's, supervision meetings and post-implementation FGD's and key informant interviews (KIIs) with community gatekeepers. These will be selected by identifying; (i) active community gatekeepers (i.e. those that detected most of the children), and; (ii) non-active community gatekeepers (based on number of cases they detected) to hear from both their experiences. We will sample these two groups based on a 1:1 ratio. These feedback meetings will be led by the clinical psychologist and supported by the project officer where a topic guide with semi structured questions regarding the barriers, facilitators and experience in using the CCDT will be used. These sessions will be conducted in their different local languages. Detailed written notes of the feedback during the supervision meetings will be collected by WCH's project officer in a structured format and digitalized after each session. The post-implementation FGDs (n=2) and KIIs (n=6) will be audio recorded, transcribed and translated for analysis.

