#### Clusters

The CCDT will be introduced and rolled-out sequentially in 28 geographically distinct zones over the course of 9 months, which are nested within five settlements. The CCDT, and proactive case detection, is implemented at zone-level. The catchment area of a community gatekeeper (i.e., the area they serve) is equal to a zone. Each zone will therefore be considered a cluster in this study. The number of gatekeepers per zone will be dependent on the population size in the zone, our aim is to train 1 gatekeeper per 3000 residents.

Four zones will transition from *pre-CCDT introduction and implementation* (i.e., the control condition) to *CCDT implementation* (i.e., intervention condition), at one-month intervals (i.e., steps), until all zones are implementing the CCDT (Intervention). The order in which the CCDT is introduced in each zone will be determined at random prior to the start of the implementation (before October, 2021). By the end of the SW-CRT period (i.e., 9 months after the start) the CCDT will be introduced and implemented in all 28 zones.

The implementation of the programme and routine detection and utilization data collection continues for the entire duration of the programme (i.e., April, 2023).

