# Sample Size

Sampling takes place at zone level. The number of children and adolescents that will be detected and that will utilize TPO's services/service points per month within each zone will be determined as primary outcome of this evaluation. Using existing utilization data, we estimated the number of zones required to detect a 20% difference in utilization rates pre- to post-CCDT implementation with at least 90% power. Among the zones for which we had existing utilization data available (n=26 zones), we estimated a mean of 17.1 initial encounters with mental healthcare per month per zone (SD=20.1, Median=11.8, IQR=4-24). We conservatively estimated utilization to equal zero in the two zones for which we had missing information. We also conducted a sensitivity analysis by imputing utilization rates for the two zones with missing data by selecting a random number from a Poisson distribution that reflected available utilization data. The intraclass correlation of utilization among zones within a settlement was estimated to be low (ICC=0.115).

Following methods developed by Woertman and colleagues [24], we estimated the minimum sample size required for parallel-groups randomized controlled trial and multiplied that value by the design effect for a stepped-wedge trial over a range of steps to estimate the number of zones required for this study [25]. Twenty-eight zones with seven steps would provide greater than 90% power to estimate a 20% difference in utilization between pre-CCDT and post-CCDT implementation. CCDT will be introduced in four zones per step (i.e., one-month each in length) and monthly utilization data will be collected from each zone the day before the next step.

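### Gatekeepers for the post-implementation interviews are classed as active or non-active on a case count that ignores months of tool use, so the label is partly confounded with roll-out step

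*Protocol*

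**What the plan says.** The Protocol's Qualitative data section (under Description of data collected) names two groups of gatekeepers for post-implementation feedback: "active community gatekeepers (i.e. those that detected most of the children), and; (ii) non-active community gatekeepers (based on number of cases they detected"). It adds: "We will sample these two groups based on a 1:1 ratio". The sample is small: "The post-implementation FGDs (n=2) and KIIs (n=6) will be audio recorded, transcribed and translated for analysis". No cut-off, time window, denominator or selection date is given.

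The roll-out is staggered. Sample Size states: "Twenty-eight zones with seven steps would provide greater than 90% power", with four zones crossing over per one-month step. Clusters states: "By the end of the SW-CRT period (i.e., 9 months after the start) the CCDT will be introduced and implemented in all 28 zones". Gatekeepers are trained in the week before their own zone's step (Training and supervision community gatekeepers). Detection data are logged "from the moment that the gatekeepers start using the CCDT, until the end of the project duration", which is April 2023 (Description of data collected). Each log entry carries a detection date.

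Feasibility is a secondary outcome with two qualitative sources: feedback at supervision sessions, and these post-implementation discussions and interviews (Secondary outcome measure; Table 1).

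**The concern.** A count of detections is a rate multiplied by time. When time differs by design, ranking on the count ranks partly on time. A gatekeeper in a seventh-step zone who is as active as a colleague in a first-step zone will have logged fewer cases and is more likely to be labelled non-active.

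The 1:1 split exists so that the team hears from people who used the tool a lot and from people who did not. To the extent that the second group contains later starters, difficulties of the first months could be read as reasons for not using the tool. With so few informants, a few misplaced gatekeepers can shift the themes reported on barriers and facilitators.

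**Working it through.** **Gap between start dates (from the Protocol).** 28 zones / 4 zones per step = 7 steps, which agrees with Sample Size. The first and last starts are (7 − 1) × 1 month = 6 months apart.

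**Months of use (partly assumed).** Assume a study start in October 2021 (Clusters sets the order of zones before that month) and one all-control month, so the first step is in November 2021 and the seventh in May 2022.

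- Selection at the end of the nine months (June 2022): 8 months of use for step 1 and 2 for step 7, ratio 8/2 = 4.
- Selection in April 2023: 18 and 12 months, ratio 18/12 = 1.5.

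**Share of the variation in counts due to start date.** Let T be months of use, r the mean detections per gatekeeper per month, and CV the coefficient of variation of the true rate between gatekeepers. With gamma-Poisson counts,

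share = r²Var(T) / { rE(T) + r²[CV²(Var(T) + E(T)²) + Var(T)] }.

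T takes seven equally spaced monthly values, so Var(T) = (7² − 1)/12 = 4. E(T) is 5 months at the end of the roll-out and 15 in April 2023. The Protocol gives neither r nor CV. With r = 1:

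- End of roll-out, CV 0.5: 4 / (5 + 0.25 × 29 + 4) = 4/16.25 = 25%.
- End of roll-out, CV 1: 4 / (5 + 29 + 4) = 4/38 = 11%.
- April 2023, CV 0.5: 4 / (15 + 0.25 × 229 + 4) = 4/76.25 = 5%.
- April 2023, CV 1: 4 / (15 + 229 + 4) = 4/248 = 1.6%.

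Over r = 0.5 to 2 the ranges are 19–29% and 9–11% at the end of the roll-out, and 4–6% and 1.5–1.7% in April 2023. If all gatekeepers had the same true rate (CV 0), the April 2023 share would be 12–35%.

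**Who would be selected.** Simulation with 196 gatekeepers (7 per zone, close to the planned maximum of 200), r = 1.5, 4,000 replicates, taking the 20 highest and 20 lowest counts. The group size of 20 and the 7 per zone are assumptions. Selection unrelated to exposure would give 3/7 = 43% in each cell.

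| Selection date | CV | Active group from steps 1–3 | Non-active group from steps 5–7 |
|---|---|---|---|
| End of roll-out | 0 | 95% | 95% |
| End of roll-out | 0.5 | 86% | 80% |
| End of roll-out | 1 | 75% | 60% |
| April 2023 | 0 | 84% | 82% |
| April 2023 | 0.5 | 64% | 57% |
| April 2023 | 1 | 55% | 48% |

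At r = 0.5 and CV 0.5 the figures are 80% and 69% at the end of the roll-out, and 62% and 55% in April 2023.

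**Effect of ranking on a rate instead.** In a matching simulation with 200 gatekeepers and r from 0.5 to 2, the top 20 by detections per month of use share 78–79% of their members with the top 20 by count in April 2023 at CV 0.5 (86–87% at CV 1). At the end of the roll-out the overlap is 51–54% at CV 0.5 (65% at CV 1).

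**The case against.** The strongest reply is that this is purposive sampling for two group discussions and six interviews. No estimate or test depends on the label, and the Protocol gives a general criterion that the team can apply sensibly when it selects. Use and logging run to April 2023, so by then even the latest gatekeepers would have about 12 months' experience and be well past the start-up phase. Gatekeepers range from teachers and health volunteers to community leaders, so their true rates will differ, and those differences will outweigh start date. Supervision feedback comes from gatekeepers in every zone, and the qualitative material is to be read alongside each gatekeeper's detection trend over time.

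Much of this stands. A reader might infer that the rule largely sorts early from late starters. The documents do not support that in general: it needs selection near the end of the roll-out, a date the Protocol does not set, or nearly equal rates among gatekeepers. A reader might also infer that truly inactive early gatekeepers would be missed. With 20 of the 196 set at 0.1 detections a month, the bottom 20 by count in April 2023 still caught over 99% of the early-step inactive ones at CV 0 and 87% at CV 0.5; capture fell to 36% only at CV 1, where many others also have very low rates. Nor does feasibility rest on these two groups alone.

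The reply does not remove the point. The interview date is not stated, and elsewhere (Sample Size and Statistical Analysis plan) the Protocol uses post-implementation for the period after a zone crosses over, so selection soon after the ninth month is compatible with the text. The direction of the distortion was also the same in every scenario tried.

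**Conclusion.** The point holds in limited form. The selection rule is an unadjusted count under a design that fixes start dates up to six months apart, so activity is partly confounded with roll-out step. The confounding is modest if gatekeepers are chosen around April 2023 (64% and 57% at CV 0.5, or 55% and 48% at CV 1, against 43%) and strong if they are chosen near the end of the nine months (86% and 80%, or 75% and 60%). These figures rest on an assumed October 2021 start with one all-control month, assumed detection rates and CVs, and assumed group sizes, so they show sensitivity and are not predictions. The consequence is confined to one of the two feasibility data sources. The primary outcome and the randomised comparison are not affected.

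**What to change.** In the Qualitative data section, replace the count by a measure that allows for exposure: rank gatekeepers on detections per month since their zone's crossover, or on detections within a common recent window in which all zones were using the tool, and then draw the 1:1 sample. State when the selection will be made.

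The cost is one or two sentences. Detection dates are already in the logbook and each zone's crossover date follows from its randomised step. Individual training dates are not listed among the recorded items, so the zone's step date is the one to use. No new data are needed.
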